We plan to enroll 67 children with hematologic malignancies (including acute myeloid leukemia, acute lymphoblastic leukemia, juvenile myelomonocytic leukemia, and myelodysplastic syndrome) at the time of HSCT at three institutions (including UCSF, All Children's Hospital, St. Petersburg, FL, and Lucile Packard Children's Hospital, Palo Alto, CA). Patients will be enrolled on the study by day +28, prior to withdrawal of immunosuppression or administration of donor lymphocyte infusion (DLI). They will have donor chimerism and minimal residual disease (MRD) testing from the peripheral blood (PB) and bone marrow (BM) on day $+28 \pm 7$ (as per standard of care). Based on risk assessment, patients will receive one cycle of low-dose azacitidine ($40\text{mg}/\text{m}^2$ IV/SC daily $\times 4$ days) alone as immunosuppression is tapered. After tapering immunosuppression, chimerism will be repeated and patients will receive up to 6 additional cycles of low-dose azacitidine. For patients who meet at high risk for relapse, azacitidine will be combined with escalating doses of DLI for a maximum of 7 cycles in total. Risk and safety assessments, including routine laboratory parameters, donor chimerism, minimal residual disease, and GHVD activity will be assessed following each cycle.

The primary outcome measures will be indicators of relapse risk and safety / toxicity. Patients will be followed for relapse as well as incidence of severe drug toxicities and acute and chronic GVHD until 2 years post-transplant. The study will be considered successful if the rate of relapse at 2 years is $<25\%$, and the incidence of Grade IV GVHD and severe drug toxicity are $<20\%$. Correlative studies will include the effect of azacitidine on T cell immune reconstitution, as well as prospective minimal residual disease estimation by gene expression / mutation panels in patients with AML.

Study Schema

Standard Risk:

- Active Grade I GVHD, OR
- Any history of >Grade II GVHD, OR
- Full Donor Chimerism AND Pre-HSCT MRD-neg AND Post-HSCT MRD-neg

High Risk:

- No GVHD or resolved Grade I GVHD, AND
- Mixed chimerism OR Pre-Tx MRD(+) OR Post-Tx MRD(+)

[figure not shown]

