Figure 1a: Schema for myeloid malignancies. Patients will be enrolled on study prior to Day +28. Chimerism from PB and BM as well as MRD will be assessed. Patients with Grade III-IV GVHD will not receive study immunomodulatory therapy. Patients meeting criteria for High-Risk designation will receive azacitidine followed by fast withdrawal of immunosuppression. Standard-Risk patients will receive azacitidine with standard withdrawal of immunosuppression. Risk assessment will be completed following withdrawal of immunosuppression, and patients will be assigned to receive azacitidine alone or azacitidine in combination with DLI based on current risk. Patients may receive up to 6 additional courses of azacitidine with or without DLI after withdrawal of immunosuppression; the addition of DLI will be guided by risk assessments done prior to each subsequent course.

Low Risk:

- Pre-Transplant Deep Sequencing (DS) MRD AND Post-Transplant DS- MRD negative ($<10^{-6}$)

Standard Risk:

- Active Grade I GVHD, OR
- Any history of >Grade II GVHD, OR
- Full Donor Chimerism AND Pre-HSCT MRD-neg AND Post-HSCT MRD-neg

High Risk:

- No GVHD or resolved Grade I GVHD, AND
- Mixed chimerism OR Pre-Tx MRD(+) OR Post-Tx MRD(+)

[figure not shown]

Figure 1b: Schema for acute lymphoblastic leukemia. Patients will be enrolled on study prior to Day +28. Chimerism from PB and BM as well as MRD (by conventional flow cytometry as well as deep sequencing when available) will be assessed. Patients with Grade III-IV GVHD will not receive study immunomodulatory therapy. Patients meeting criteria for High-Risk designation will receive azacitidine followed by fast withdrawal of immunosuppression. Standard-Risk patients will receive azacitidine with standard withdrawal of immunosuppression. Low-Risk patients will not receive study immunomodulatory intervention and will be treated per local SOP. Risk assessment will be completed following withdrawal of immunosuppression, and patients will be assigned to receive standard therapy, azacitidine alone, or azacitidine in combination with DLI based on current risk. Patients may receive up to 6 additional courses of azacitidine with or without DLI after withdrawal of immunosuppression; the addition of DLI will be guided by risk assessments done prior to each subsequent course.

Table of Contents

Section No.		Page No.
1.0	Background and Rationale.....	10

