1.11 Preliminary data

Our group has been studying the use of subset chimerism testing and pre-emptive immunotherapy with fast withdrawal of immunosuppression (FWI) and donor lymphocyte infusion (DLI) since 2005. Our prospective multi-institutional study evaluated the feasibility of longitudinal chimerism testing in a central laboratory (including WB, CD3+, and leukemia-specific lineage chimerism) in patients with a variety of hematologic malignancies, and evaluated the feasibility of fast withdrawal of immunosuppression based on WB chimerism results. Centralized chimerism testing was feasible and showed low inter-assay variability. Increasing mixed chimerism (MC) in WB was not useful as a predictor of relapse in our study. The presence of full donor chimerism in WB, CD3+ and leukemia-specific lineages on all measurements was related to a significantly lower risk of relapse than the presence of MC in either subset (11% vs 71%, respectively; P=0.03). Increasing host chimerism in leukemia-specific lineage heralds relapse, but it was not detected early enough to allow immunotherapy. The conclusion of the study was that the goal of preemptive immunotherapy should be to achieve full donor chimerism in WB in CD3+ and leukemia-specific lineages, in an effort to prevent relapse before donor chimerism declines (40).

In a recent prospective UCSF analysis, 43 children (25 AML, 18 ALL,) underwent myeloablative BMT or PBSCT followed by immunomodulatory therapy (IT) between 2009 and 2012 (44). Patients with FDC in BM and PB at day 30 or evidence of GVHD were assigned to observation only (N=12). Patients with mixed chimerism (regardless of MRD) were assigned to intervention. Intervention consisted of fast withdrawal of immunosuppression (FWI) in 26 patients; 14 of these also received DLI. Five patients could not be assigned due to early death or relapse. Overall survival at a median of 30 months was 54%. Toxicity was acceptable, with an acute GVHD rate of 19% in the intervention arm, and a toxic death rate of 4%. Relapse was observed in 10/38 patients; 8 of the 10 relapses occurred in the intervention arm (associated with mixed chimerism). Four of these occurred late at >24 months post-transplant.

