8.4 Sample size

- 8.4.1 The sample size is estimated using Bayesian sequential monitoring design with toxicity and response outcomes as multiple endpoints(45). It is assumed that the rate of relapse in pediatric acute leukemia post-transplant would be 40% (as shown in our pilot study), azacitidine +/- DLI would reduce the 2-year relapse rate by approximately 40% to a rate of 25%. A sample size of 67 evaluable patients is required to provide 80% power at a one-sided significance level of 0.05 to test the hypothesis based on the relapse rate of H0: relapse rate > 40% (historically-controlled) versus Ha: relapse rate < 25% (treatment-targeted). The study will enroll patients until accrual of 67 patients is achieved.
- 8.4.2 Enrollment of 67 patients will be attainable with enrollment at multiple centers. Investigators from All Children's Hospital, Lucille Packard Children's Hospital have written letters of support expecting to enroll 30-40 patients over 2 years.

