8.5 Estimated Duration of the Study

- 8.5.1 67 patients are expected to enroll; enrollment over 2 years is anticipated. Study intervention and data collection (2 years) are expected to be completed by 4 years. Preliminary safety analysis will be available within 1 year.

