8.7 Interim analysis and stopping rules for safety and efficacy

- 8.7.1 As a phase II study with 67 evaluable patients, the study is designed to have interim stopping rules based on the safety/toxicity evaluation (including death and incidence of severe GVHD). See Section 11.0 for reporting SAEs associated with study stopping rules.
- 8.7.2 The occurrence of any serious adverse events (SAEs) will be reported to the Coordinating Trial Center within 24 hours of learning about them, and within 10 days in writing. See Section 11.0 for SAE definitions and reporting requirements. A rate of SAEs of up to 20% is deemed acceptable in view of the potential benefit of the therapy. Accrual will stop if 3 patients with SAEs are observed in the first 3-6 patients undergoing the intervention, if 4 patients with SAEs are observed in the first 7-9 patients undergoing the intervention, or if 5 patients with SAEs are observed in the first 10-13 patients undergoing the intervention. The following table displays the minimum

number of SAEs for the study to be stopped at each accrual period and the probability of early stopping at the assumed SAE rate.

Patients on Study	4-6	7-9	10-13	14-17	18-21	22-27
Number of patients with SAE	≥3	≥4	≥5	≥6	≥7	≥8
15%SAE	1.2%- 4.2%	1.1%- 2.8%	0.9%- 2.7%	0.9%- 2.4%	0.9%- 2.0%	0.8%- 2.6%
20%SAE	2.6%- 8.2%	2.9%- 6.6%	2.6%- 6.9%	3.2%- 6.8%	3.5%- 6.6%	3.6%- 8.2%
25%SAE	4.7%- 13.2%	5.8%- 11.7%	5.8%- 12.6%	7.3%- 12.8%	8.2%- 12.7%	8.9%- 14.2%

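### Section 8.4.1 sets 80% power on 67 evaluable patients but stops accrual at 67 enrolled, so the stated power holds only if almost no patient is lost from the analysis

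*Combined protocol and SAP*

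**What the plan says.** Section 8.4.1 gives the requirement: "A sample size of 67 evaluable patients is required to provide 80% power at a one-sided significance level of 0.05". The hypotheses are "H0: relapse rate > 40% (historically-controlled) versus Ha: relapse rate < 25% (treatment-targeted". The paragraph closes with the accrual rule: "The study will enroll patients until accrual of 67 patients is achieved".

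Elsewhere the same number is used in both senses:

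- The summary at the front of the protocol: "We plan to enroll 67 children with hematologic malignancies".
- Section 8.5.1: "67 patients are expected to enroll; enrollment over 2 years is anticipated".
- Section 8.7.1: "As a phase II study with 67 evaluable patients".

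No section defines evaluable, allows for dropout or provides for replacement. Three other parts of the protocol bear on who is counted:

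- **Section 5.7.** A patient whose azacitidine is held for more than 6 weeks stays on study but goes into a separate safety and efficacy analysis. Section 5.7.6 does the same for a patient given DLI without azacitidine in cycles 2 to 7.
- **Section 4.1.** Enrolment occurs before day +28, while the first risk assignment rests on tests done between day +21 and day +42 (section 5.2.2).
- **Section 1.11.** In the sponsor's pilot of 43 children, "Five patients could not be assigned due to early death or relapse", and relapse was reported as 10/38.

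**The concern.** The number required for analysis and the number at which enrolment ends are equal, so the plan works as stated only if every enrolled patient is evaluable. The protocol gives reasons to expect otherwise: it already removes some enrolled patients from the main efficacy analysis, and its own precedent dropped 5 of 43 from the relapse denominator.

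Two things are at stake. First, a result that fails to show the target reduction could be reported as coming from a trial with 80% power when the power was lower. Second, with evaluable undefined, the denominator of the primary efficacy endpoint could be settled after outcomes are known.

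**Working it through.** **Inputs.** Null relapse rate p0 = 0.40, target p1 = 0.25, one-sided alpha 0.05, power 0.80, n = 67 evaluable (all section 8.4.1). Pilot loss 5/43 = 0.116 (section 1.11). The Bayesian sequential design named in 8.4.1 cannot be rerun because its priors and cut-offs are not given. The stated power and alpha are frequentist and can be checked with a one-sample binomial test.

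**Step 1: reproduce 67.**

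Uncorrected normal formula:

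n0 = [(1.645 × √0.24 + 0.842 × √0.1875) / 0.15]² = 60.9, that is 61 patients. This does not reproduce 67.

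With continuity correction:

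n = (n0/4) × [1 + √(1 + 2/(n0 × 0.15))]² = 67.4, that is 68 after rounding up, within one patient of 67.

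Power at n = 67 with continuity correction:

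z = [(0.15 − 1/134) × √67 − 1.645 × √0.24] / √0.1875 = (1.167 − 0.806)/0.433 = 0.833, so power = 0.798.

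Exact binomial at n = 67: reject H0 at 19 or fewer relapses; alpha = 0.0324, power = 0.784.

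So 67 evaluable patients give 78% (exact) to 80% (corrected normal). The plan's figure stands.

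**Step 2: apply the pilot loss (assumed to carry over).**

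Expected evaluable = 67 × 38/43 = 59.2, about 59.

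Corrected normal at 59: z = [(0.15 − 1/118) × √59 − 0.806]/0.433 = (1.087 − 0.806)/0.433 = 0.650, so power = 0.742.

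Exact power moves in a saw-tooth between neighbouring n, so a single point misleads:

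| Evaluable n | Reject at or below | Alpha | Exact power |
|---|---|---|---|
| 57 | 16 | 0.042 | 0.758 |
| 58 | 16 | 0.034 | 0.733 |
| 59 | 16 | 0.028 | 0.707 |
| 60 | 17 | 0.041 | 0.775 |
| 61 | 17 | 0.034 | 0.751 |
| 62 | 18 | 0.049 | 0.812 |

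The number evaluable is itself random, so a fairer summary averages exact power over it:

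Average power = Σ over m of C(67, m) × (1 − d)^m × d^(67 − m) × exact power(m), where d is the loss rate.

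At d = 5/43 this gives 0.748.

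**Step 3: range over the loss rate.**

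| Loss rate d | Expected evaluable of 67 | Averaged exact power |
|---|---|---|
| 0 | 67 | 0.784 |
| 1/43 = 2.3% | 65.4 | 0.800 |
| 2/43 = 4.7% | 63.9 | 0.794 |
| 3/43 = 7.0% | 62.3 | 0.781 |
| 4/43 = 9.3% | 60.8 | 0.765 |
| 5/43 = 11.6% (pilot) | 59.2 | 0.748 |
| 20% (assumed) | 53.6 | 0.70 |

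The small rise from 0 to 2.3% loss is the saw-tooth, since n = 67 lies at a low point. The uncorrected normal formula would give 0.788 at n = 59, but it needs only 61 patients and is not the calculation behind 67.

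**The case against.** The strongest reply is that no arithmetic in 8.4.1 fails and that the pilot loss may not carry over. Much of this stands.

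- **The five pilot losses were early deaths or relapses, and the split is not given.** Relapse is the primary endpoint, so a relapse after enrolment is an event, not a missing value. The pilot counted from transplant, whereas enrolment here can be as late as day +28, so some early losses could fall before enrolment. If only 1 or 2 per 43 are true losses, power is 79% to 80%, essentially as stated.
- **Accrual of 67 might be meant as 67 evaluable**, since 8.7.1 uses that phrase. But the front summary and 8.5.1 both speak of 67 enrolled, so the wording does not settle it.
- **The test used here is a stand-in.** Section 8.6.2 plans only proportions with 95% confidence intervals, so the critical values above are not protocol rules. They check the stated power and nothing more.

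A reader might infer more than the documents support, in three ways:

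- **That power falls to 71%, or to 64% with about 50 evaluable.** Those are the exact values at n = 59 and n = 50, and both are troughs of the saw-tooth. A loss of a quarter, which would leave about 50, has no source in the documents.
- **That untreated patients are plain attrition.** The schema says "Patients with Grade III-IV GVHD will not receive study immunomodulatory therapy", and Low-Risk ALL patients also receive no study intervention. But objective 2.1.1 evaluates the risk-adaptive approach as a whole, Low Risk is one of its strata (5.3.4), and section 5.12 follows all patients for two years. Their relapse status is observed, and they can be counted.
- **That evaluable should mean relapse-free and risk-assigned at the day +21 to +42 assessment.** That would remove early relapses, which are primary events, while the 40% null stays unchanged, and so would favour the treatment. On the pilot's reduced denominator relapse was already 10/38 = 26%.

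What survives is the gap between enrolled and evaluable, made concrete by the separate-analysis rules in 5.7 and 5.7.6.

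**Conclusion.** The point holds as a gap in specification with a modest effect on power. The 67 is correctly derived as a number of evaluable patients, but the plan enrols that same number with no margin and diverts some enrolled patients from the main efficacy analysis. The stated 80% is therefore secure only if almost nobody is excluded. At the pilot's loss rate power is about 75%, some 5 points below the claim; at an assumed 20% loss it is about 70%.

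These figures rest on three assumptions: a one-sample test of 40% against 25% at one-sided 0.05; losses that leave the denominator independently of outcome; and a loss rate that the documents do not give for this trial. They do not show that the trial will be under-powered. They show that the plan cannot say whether it will be until the analysis set is fixed.

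**What to change.** In section 8.4.1:

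1. Define the primary relapse analysis set as all enrolled patients, and count every relapse after enrolment as an event, including those before risk assignment.
2. Keep the separate analyses in sections 5.7 and 5.7.6 (azacitidine held more than 6 weeks; DLI without azacitidine) as supplementary, with those patients also in the primary set.
3. If any patients are to be excluded, list the categories in advance and replace the 80% with the power for the number expected from 67 enrolled: about 75% at the pilot's 38/43 yield.
4. Use the same term, enrolled or evaluable, in the front summary and in sections 8.4.1, 8.5.1 and 8.7.1.

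The cost is wording and, if exclusions remain, a slightly less favourable stated power. No extra patients are needed. Should the sponsor prefer exclusions and 67 evaluable, accrual would have to be 67 × 43/38 = 75.8, or 76 (averaged exact power 0.81), but the correction does not depend on that.

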8.5 Estimated Duration of the Study

- 8.5.1 67 patients are expected to enroll; enrollment over 2 years is anticipated. Study intervention and data collection (2 years) are expected to be completed by 4 years. Preliminary safety analysis will be available within 1 year.

8.6 Statistical Analysis

- 8.6.1 Patient demographics and baseline characteristics including age, sex, race, ethnicity and medical conditions will be summarized using descriptive statistics. For quantitative parameters, descriptive statistics will include the mean, standard deviation, minimum, median and maximum. For qualitative parameters, descriptive statistics will include the frequency and proportions.
- 8.6.2 The primary endpoint parameters: (1) relapse rate and (2) incidence of Grade III-IV aGVHD, severe cGVHD, and Grade IV toxicities, will be estimated using proportions with 95% CI.
- 8.6.3 The chimerism parameters (CD3+, CD14/15+, CD19+, CD33+, CD34+) and incidence of acute and chronic GVHD will also be analyzed using descriptive statistics including means, standard deviation and 95% CI.

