8.3 Primary Safety Endpoint Definitions

- 8.3.1 National Cancer Institute CTCAE version 4.0 grade 3 or higher renal, hepatic, cardiac, pulmonary, or neurologic toxicity;
- 8.3.2 Grade III/IV acute GVHD or Severe/Extensive chronic GVHD
- 8.3.3 Serious infection
- 8.3.4 Severe hematologic toxicity/ graft failure
- 8.3.5 >2 dose reductions for any reason.

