11.18 Classification of GVHD

To be classified as severe cGVHD, a minimum of 3 organs should be involved with stage 2 disease, or 2 organs with stage 3 disease. Please see Appendix 2 for a list of symptoms and staging. (For example: skin: 10 – 50% skin rash; Joint: mild joint contractures; and esophagus: dysphagia or odynophagia requiring dietary changes would qualify for severe cGVHD. Multiple symptoms within the same organ system should not be counted. Rash, sclerodermatous changes and dry flaky skin would all count as 1 organ/system involvement).

11.19 Hematopoietic toxicity:

- 11.4.4 Grade 3: ANC >500/microliter but < 1000/microliter for a duration of > 4 weeks. Platelets < 50,000/microliter but > 20,000/microliter for a duration of > 4 weeks.
- 11.4.5 Grade 4: neutrophils <500/microliter and/or platelets <20,000/microliter for a duration of > 4 weeks.
- 11.4.6 Grade 5: death due to bacterial or fungal infection or hemorrhage associated with hematopoietic toxicity.

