EYES Mean tear test (mm):  >10  6-10  ≤5  Not done		 No symptoms	 Mild dry eye symptoms not affecting ADL (requiring eyedrops ≤ 3 x per day) OR asymptomatic signs of keratoconjunctivitis sicca	 Moderate dry eye symptoms partially affecting ADL (requiring drops > 3 x per day or punctal plugs), WITHOUT vision impairment	 Severe dry eye symptoms significantly affecting ADL (special eyewear to relieve pain) OR unable to work because of ocular symptoms OR loss of vision caused by keratoconjunctivitis sicca
GI TRACT		 No symptoms	 Symptoms such as dysphagia, anorexia, nausea, vomiting, abdominal pain or diarrhea without significant weight loss (<5%)	 Symptoms associated with mild to moderate weight loss (5-15%)	 Symptoms associated with significant weight loss >15%, requires nutritional supplement for most calorie needs OR esophageal dilation
LIVER		 Normal LFT	 Elevated Bilirubin, AP*, AST or ALT <2 x ULN	 Bilirubin >3 mg/dl or Bilirubin, enzymes 2-5 x ULN	 Bilirubin or enzymes > 5 x ULN

	SCORE 0	SCORE 1	SCORE 2	SCORE 3
LUNGS[†]	 No symptoms	 Mild symptoms (shortness of breath after climbing one flight of steps)	 Moderate symptoms (shortness of breath after walking on flat ground)	 Severe symptoms (shortness of breath at rest; requiring O ₂)
FEV1 				
DLCO 	 FEV1 > 80% OR LFS=2	 FEV1 60-79% OR LFS 3-5	 FEV1 40-59% OR LFS 6-9	 FEV1 ≤39% OR LFS 10-12
JOINTS AND FASCIA	 No symptoms	 Mild tightness of arms or legs, normal or mild decreased range of motion (ROM) AND not affecting ADL	 Tightness of arms or legs OR joint contractures, erythema thought due to fasciitis, moderate decrease ROM AND mild to moderate limitation of ADL	 Contractures WITH significant decrease of ROM AND significant limitation of ADL (unable to tie shoes, button shirts, dress self etc.)

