GENITAL TRACT	 No symptoms	 Symptomatic with mild signs on exam AND no effect on coitus and minimal discomfort with gynecologic exam	 Symptomatic with moderate signs on exam AND with mild dyspareunia or discomfort with gynecologic exam	 Symptomatic WITH advanced signs (stricture, labial agglutination or severe ulceration) AND severe pain with coitus or inability to insert vaginal speculum

Other indicators, clinical manifestations or complications related to chronic GVHD (check all that apply and assign a score to its severity (0-3) based on its functional impact where applicable (none – 0,mild -1, moderate -2, severe – 3)

Esophageal stricture or web _____ Pericardial Effusion _____ Pleural Effusion(s) _____
 Ascites (serositis) _____ Nephrotic syndrome _____ Peripheral Neuropathy _____
 Myasthenia Gravis _____ Cardiomyopathy _____ Eosinophilia > 500µl _____
 Polymyositis _____ Cardiac conduction defects _____ Coronary artery involvement _____
 Platelets <100,000/µl _____ Progressive onset _____

OTHERS: Specify: _____

19.3 Appendix 3: Use of Donor Lymphocyte Infusions or Hematopoietic Progenitor Cell Boosts after Hematopoietic Progenitor Cell Transplant (HSCT)

Implementation date: [REDACTED]	Obsolete date: _____
Review dates: [REDACTED]-new [REDACTED]	
Revision dates: [REDACTED]	

1.0 Objective:

1.1 To provide guidelines for use of Donor Lymphocyte Infusions (DLI) and hematopoietic progenitor cell boosts after transplant for patients in whom DLI is not performed on an investigational study.

2.0 Scope:

2.1 PBMT attending physicians, fellows, nurse specialists, and PBMT laboratory staff.

3.0 Materials/Equipment:

None

4.0 Definitions:

4.1 **"Additional donor cells"**: Donor lymphocyte infusion (DLI) and/or hematopoietic progenitor cell boost.

4.2 **aGvHD**: Acute graft vs. host disease

4.3 **DLI: Donor lymphocyte infusion**: Infusion of additional donor's cells into bone marrow transplant recipients with the goal to enhance graft-versus-leukemia effect or speed up immune reconstitution in recipients of T-cell depleted (TCD) transplants.

4.4 Therapeutic DLI – DLI used for the treatment of relapse (in malignancies) or treatment of infection (in malignancies or non-malignant disorders).

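### The primary safety endpoint names severe or extensive chronic GVHD, but the analysis counts only severe disease under a multi-organ rule that leaves out a child with one organ at the worst score

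*Combined protocol and SAP*

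**What the plan says.** Five places in the combined protocol and SAP bear on this.

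- **8.3 (primary safety endpoint definitions).** Item 8.3.2 is "Grade III/IV acute GVHD or Severe/Extensive chronic GVHD". Item 8.3.1 is CTCAE toxicity of grade 3 or higher in five systems: kidney, liver, heart, lung and nervous system.
- **8.6.2 (analysis).** The safety parameter, estimated by proportions with 95% CI, is the "incidence of Grade III-IV aGVHD, severe cGVHD, and Grade IV toxicities".
- **11.18 (classification).** Severe chronic GVHD means that "a minimum of 3 organs should be involved with stage 2 disease, or 2 organs with stage 3 disease". For staging it says "Please see Appendix 2 for a list of symptoms and staging", and it adds that "Multiple symptoms within the same organ system should not be counted".
- **Appendix 2 (scoring form).** Each organ is scored 0 to 3. Score 3 for the eyes includes "loss of vision caused by keratoconjunctivitis sicca". For skin it includes deep, hidebound sclerosis, and for joints it means contractures with marked loss of movement and daily function. For a separate list of other manifestations, the form asks the assessor to "assign a score to its severity (0-3) based on its functional impact where applicable", with 3 labelled severe.
- **8.6.3.** All acute and chronic GVHD is also summarised, descriptively.

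**The concern.** The endpoint definition and the analysis do not name the same event. The analysis takes the narrower term, and the only definition of that term is a multi-organ rule. Under that rule a child disabled by chronic GVHD in one organ is not a severe case. Three organs at stage 2 are a severe case, and the example in 11.18 is a rash, mild contractures and swallowing difficulty that changes the diet.

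Chronic GVHD is a recognised harm of withdrawing immunosuppression and giving DLI, and the protocol follows it to two years. Any omission of this kind works in one direction: it lowers the reported severe chronic GVHD proportion.

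**Working it through.** The plan states no figure that depends on this definition, so there is none to reproduce. The check is to apply the rule, look for other routes into the endpoint, and size the effect per child.

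**1. The terms side by side**

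| Section | Role | Chronic GVHD term |
|---|---|---|
| 8.3.2 | endpoint definition | severe or extensive |
| 8.6.2 | analysis | severe |
| 11.16.2 | event that may trigger stopping rules | severe |
| 11.18 | definition | severe only; *Extensive* is not defined here or elsewhere |

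**2. The 11.18 rule applied to organ scores.** Reading stage as Appendix 2 score, a child is severe if at least three organs score 2 or more, or at least two organs score 3.

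| Organ scores | Severe under 11.18? |
|---|---|
| 3 | no |
| 3, 1 | no |
| 3, 2 | no |
| 3, 2, 1, 1, 1 | no |
| 2, 2 | no |
| 2, 2, 2 | yes |
| 3, 2, 2 | yes |
| 3, 3 | yes |

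One organ at the maximum is not severe, even with a second organ at score 2. Several signs in one organ cannot make up the difference, because they count once.

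**3. Other routes into the endpoint**

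- *Through 8.3.1.* Eye, skin and joint are not among the five systems. Liver and lung are. For example, 6.2.4 equates grade III hepatotoxicity with AST/ALT above 5 times the upper limit, which is also within liver score 3 in Appendix 2. Even so, 8.6.2 carries forward only Grade IV toxicities, so a grade 3 event under 8.3.1 does not reach that estimate.
- *Through Grade IV toxicities in 8.6.2.* There is no organ limit, so a case graded IV would enter there. The documents do not say how single-organ eye, skin or joint disease would be graded. For events not listed in CTCAE, 11.9 places disabling events at Grade 3 and life-threatening events at Grade 4.
- *Through 8.3.2.* This is undetermined, because *Extensive* has no definition.

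**4. Stage against score.** 11.18 speaks of stages and Appendix 2 of scores, and no mapping is given. They do not line up for skin: the 11.18 example treats a rash over 10–50% as stage 2, whereas Appendix 2 gives score 1 below 18% of body surface and score 2 at 19–50%. A rash over 15% is thus stage 2 by the example and score 1 on the form.

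**5. Size.** With the planned 67 patients as denominator, m uncounted children lower the chronic GVHD proportion by m/67. The documents give no rate of single-organ score-3 disease, so m = 1 to 5 is an assumed range.

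| m (assumed) | m/67 | Understatement |
|---|---|---|
| 1 | 0.0149 | 1.5 points |
| 3 | 0.0448 | 4.5 points |
| 5 | 0.0746 | 7.5 points |

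**The case against.** The best defence has four parts.

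- **A multi-organ definition is a legitimate choice.** This stands. One organ rated severe is not the same as disease classed severe overall, and the severe label for level 3 in Appendix 2 is attached to the list of other manifestations. But 8.3.2 is worded more widely than 8.6.2, so the plan does not show that the exclusion was intended.
- **The children are not hidden.** This largely stands. 8.6.3 summarises all chronic GVHD with a 95% CI, and 6.1 requires every case in the intervention group to be reported within 10 days. Neither separates single-organ score-3 disease from mild disease.
- **Stopping rules and urgent reports.** A reader might infer that these children also disappear from the stopping-rule counts and the 24-hour reports. The documents do not support that. The definition of serious in section 11 includes hospitalization and lasting or significant incapacity, in the judgement of the study PI. Sections 8.7.2 and 11.14 require SAEs to be reported within 24 hours, and the tables in 8.7.2 and 8.7.3 count patients with SAEs. Disabling single-organ disease may well enter by that path.
- **The 20% success limit.** A reader might also start from 13/67 = 19.4%, add one child to get 14/67 = 20.9%, and conclude that the omission could turn failure into success. The criterion in the protocol summary concerns Grade IV GVHD and severe drug toxicity. It does not name chronic GVHD, which 11.18 stages rather than grades I to IV. Section 8.6.2 sets no limit and does not say that its events form one composite. That crossing matches no stated decision.

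**Conclusion.** The point holds for the analysed endpoint. Sections 8.3.2 and 8.6.2 name different events, one term is undefined, and the chronic GVHD proportion in 8.6.2, read with 11.18, leaves out a child with one organ at score 3. It can understate disabling chronic GVHD by 1.5 percentage points per such child out of 67.

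This rests on three assumptions: that stage 3 in 11.18 means score 3 in Appendix 2, which is a reasonable reading but is not stated; that the denominator is 67; and, if 8.6.2 is read as a composite, that the child has no other counted event. How many children are affected cannot be derived from the documents. No claim is made about stopping-rule events, 24-hour reports or the 20% criterion. The change should be made, because it is cheap and bears on a primary safety estimate.

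**What to change.** 1. Use one defined chronic GVHD term in 8.3.2, 8.6.2 and 11.16.2, and either define *Extensive* or remove it.
2. State in 11.18 how stages map to Appendix 2 scores, and reconcile the skin cut-offs (10–50% against 19–50% of body surface).
3. For the endpoint analysis, count any child with at least one organ at Appendix 2 score 3, or at least three organs at score 2.
4. If the sponsor keeps the multi-organ rule, report the proportion with single-organ score-3 disease, with its 95% CI, beside the primary safety proportion.

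The cost is wording in those sections. The organ scores are already on the Appendix 2 form, so no new data are needed. The downside is that the reported chronic GVHD rate may be slightly higher. This concerns which children are counted in the endpoint and proposes no change to treatment.
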